8.2 Statistical Analysis Principle

SAS (version 9.2 or above) or R is used in this study for statistical analysis.

Measurement data are presented as the number of cases, mean±standard deviation, median, minimum, maximum, and quartiles. Count data are presented as frequencies and percentages. Parametric methods are first considered for statistical tests, and non-parametric methods are used if the data distribution differs significantly from the distribution assumed by the statistical test.

A two-sided hypothesis test is used for difference test, and the alpha level is set to 0.05 (two-sided); that is, if the p-value is <0.05, the difference is considered statistically significant.

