3.1 Purpose of the Clinical Trial

Through this real-world study, to analyze the response of functional constipation patients with different severity, treatment status, capsule dosage, and combined medication to Vibrabot capsule, as well as the duration of efficacy maintenance during the follow-up period; to compare the efficacy with patients treated with drugs or other therapies during the same period, explore the possibility of curing functional constipation patients, further improve the treatment satisfaction of constipation patients, and promote the establishment and application of consensus or guidelines for the use of Vibrabot capsule in treating functional constipation.

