3.2 Content of the Clinical Trial

This study is a multi-center clinical trial. Patients are considered eligible for this study if they meet the inclusion criteria and do not meet any of the exclusion criteria. This study plans to include 300 patients with chronic functional constipation to treat with Vibrabot capsules for at least 6 weeks, and ≥ 300 patients with constipation receiving

other treatments concurrently. The patients, based on their treatment needs and preferences, and after comprehensive consideration by clinical doctors, will undergo vibrating capsule treatment, other treatments, or combination therapy. After entering the study, patients should maintain stable dietary intake (including high-fiber diet, fiber supplements, probiotics, etc.) and exercise according to the recommendations of the constipation diagnosis and treatment guidelines.

During the entire clinical study period, patient-related information will be collected according to the specified time points in the protocol to evaluate the response of functional constipation patients with different severity levels to Vibrabot capsules.

Patients are considered eligible for this study if they meet the inclusion criteria and do not meet any of the exclusion criteria. This study plans to include 300 patients with chronic functional constipation to treat with Vibrabot capsules for at least 6 weeks or more.

The patients, based on their treatment needs and preferences, and after comprehensive consideration by clinical doctors, will undergo vibrating capsule treatment. After entering the study, patients should maintain stable dietary intake (including high-fiber diet, fiber supplements, probiotics, etc.) and exercise according to the recommendations of the constipation diagnosis and treatment guidelines.

4. Background of the Clinical Trial

Constipation is characterized by a decrease in bowel movements, dry and hard stools, and difficulty in defecation. With changes in diet, faster pace of life, and social psychological factors, the prevalence of chronic constipation is on the rise. The global incidence of chronic constipation is 14%, while the prevalence of chronic constipation in adults in China is 4.0% to 10.0%. The prevalence of functional constipation in China is 6%. The high-risk groups for constipation include the elderly, women,

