6.2 Exclusion Criteria

1. People who are not eligible for surgery or refuse to undergo any abdominal surgery;
2. People with known or suspected gastrointestinal obstruction, stenosis, diverticulum, bleeding, malformation, and fistula.
3. People allergic to polymeric materials;

4. People implanted with cardiac pacemakers and using gastrointestinal pacemakers;
5. People with abdominal aortic aneurysms, gastrointestinal vascular lesions, ulcers, and lesions with bleeding tendencies.
6. People with dysphagia;
7. Pregnant women;
8. People with severe depression and anxiety and severe acute gastrointestinal lesions.
9. People with other conditions, so the investigator considers them not eligible for this study.

7 . Overall Design

This study is a multi-center, prospective cohort study based on real-world clinical trial design, planning to include 300 patients with chronic functional constipation to treat with Vibrabot capsules, and concurrently include ≥ 300 patients with functional constipation to treat by other methods.

During the study, it is necessary to collect the patient's basic information, baseline constipation status and treatment information, capsule intake during treatment, and concomitant medication. During the treatment phase, patients follow the doctor's advice to receive Vibrabot capsule treatment and maintain stable dietary intake and exercise according to the constipation diagnosis and treatment guidelines.

During the study, the patients need to scan the QR code or search for the electronic questionnaire "Vibrabot Health" Official Account on WeChat, and fill in the relevant information during the treatment in the electronic questionnaire in a timely and truthful manner. The treatment effect of the patients is evaluated by assessing the number of occurrences of spontaneous bowel movements (SBM) and complete spontaneous bowel movements (CSBM).

Note:

[figure not shown]
Spontaneous bowel movement: No medication used within 24 hours before bowel movement.

Spontaneous bowel movement: No medication was used within 24 hours before defecation, and there is a feeling of complete fecal evacuation.

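### Comparing the capsule with other therapies is a stated purpose in self-selected patients, but the plan designates no between-group endpoint, does not place combination patients in that contrast, and gives no confounding control

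*Combined protocol and SAP*

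**What the plan says.** All references are to the combined protocol and SAP.

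- **Purpose.** The Protocol Summary and Section 3.1 include the aim "to compare the efficacy with patients treated with drugs or other therapies during the same period". The flow chart in 7.1.1 also lists comparison with other methods as an output.
- **Cohorts.** Section 7 plans 300 capsule patients and will "concurrently include ≥ 300 patients with functional constipation to treat by other methods".
- **How treatment is chosen.** Section 3.2 says patients are treated "based on their treatment needs and preferences, and after comprehensive consideration by clinical doctors", and that they "will undergo vibrating capsule treatment, other treatments, or combination therapy". A second, overlapping paragraph in 3.2 mentions the capsule only: they "will undergo vibrating capsule treatment. After entering the study, patients should maintain stable dietary intake".
- **Endpoints.** The primary endpoint (7.2.1) is a response rate against 50% in patients using the capsule alone. Several of the ten secondary endpoints in 7.2 could be computed in both cohorts (items 3 and 5 to 8, for example), but none is worded as a contrast between them.
- **Definitions.** The Note in Section 7 defines a spontaneous movement, "Spontaneous bowel movement: No medication used within 24 hours before bowel movement", and a complete one, "No medication was used within 24 hours before defecation, and there is a feeling of complete fecal evacuation".
- **Analysis.** Section 8.1 sizes the study as a single group, and its full analysis set pools capsule and other-treatment patients without a rule for assigning them to groups. Section 8.2 gives descriptive summaries, a preference for parametric over non-parametric tests, and "A two-sided hypothesis test is used for difference test, and the alpha level is set to 0.05 (two-sided"). Matching, weighting, stratification and covariate adjustment of a group comparison appear nowhere.

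**The concern.** When need, preference and physician judgement decide treatment, the groups can differ in severity, constipation type and treatment history before the first dose. A simple test then mixes the treatment effect with case mix, and the direction of the error cannot be known in advance. With endpoint, grouping and adjustment all open, each can also be chosen after the data are seen. The stated purpose extends to consensus or guideline use of the capsule, so a biased comparison could be carried forward.

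There is a second, conditional problem of measurement. If medication prescribed as the comparator treatment counts under the 24-hour rule, movements in patients taking drugs may not qualify as spontaneous. Their CSBM response could then be under-counted for reasons unrelated to benefit, and adjustment for baseline factors would not repair that.

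**Working it through.** **1. Does the plan's own sample size support the comparison?** Inputs from 8.1: null rate 0.40, expected rate 0.50, alpha 0.05, power 0.80, 20% loss. With the two-sided 1.96:

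n = [1.96·√(0.40·0.60) + 0.8416·√(0.50·0.50)]² / 0.10² = 190.7, so 191; and 191/0.80 = 238.75, so 239.

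Both stated figures reproduce. The calculation has no comparator input, so it neither sizes nor specifies a between-group contrast.

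**2. What would an unadjusted test do under case-mix imbalance?** The documents give no severity split and no response by severity, so all of these inputs are assumptions. Response in a group = s·r_sev + (1 − s)·r_mild, where s is the share of severe patients. I take r_sev/r_mild = 0.40/0.60 (20-point gap) or 0.45/0.55 (10-point gap), and no treatment effect. The test is a two-proportion z test:

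P(reject) = Φ[(d − 1.96·SE₀)/SE₁] + Φ[(−d − 1.96·SE₀)/SE₁]

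Here d is the absolute difference, SE₀ the pooled standard error and SE₁ the unpooled one.

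Example, severe share 30% (capsule) v 60% (other), 20-point gap, 300 per group:
- capsule 0.30·0.40 + 0.70·0.60 = 0.54; other 0.60·0.40 + 0.40·0.60 = 0.48; d = 0.06
- SE₀ = √(2·0.51·0.49/300) = 0.0408; SE₁ = √[(0.54·0.46 + 0.48·0.52)/300] = 0.0407
- (0.06 − 0.0800)/0.0407 = −0.49, so P(reject) = 0.312, nearly all of it falsely favouring the capsule.

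| Severe share, capsule v other | 20-point gap: rates | n = 300 | n = 240 | 10-point gap: rates | n = 300 | n = 240 |
|---|---|---|---|---|---|---|
| 40% v 50% | 0.52 v 0.50 | 8% | 7% | 0.51 v 0.50 | 6% | 6% |
| 35% v 55% | 0.53 v 0.49 | 16% | 14% | 0.515 v 0.495 | 8% | 7% |
| 30% v 60% | 0.54 v 0.48 | 31% | 26% | 0.52 v 0.49 | 11% | 10% |

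The nominal rate is 5%, and n is per group. The figure 240 is 300·0.80. Section 8.1 applies its 20% loss to the single-group calculation, so using it for both cohorts is my assumption.

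**3. The opposite direction.** Assume a true 10-point benefit, a 20-point gap, and the more severe patients in the capsule group (50% v 40%, 55% v 35%, 60% v 30%). The rates are 0.60 v 0.52, 0.59 v 0.53 and 0.58 v 0.54. Power at 300 per group is 51%, 32% and 17%, against 69% with balanced groups (0.61 v 0.51). At 240 it is 42%, 26% and 14%, against 60%.

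**4. Combination patients.** Section 7.2.1 restricts the primary endpoint to patients using the capsule alone, so combination patients are outside it. Sections 3.2 and 7.1.1 recognise combination as a category, and 3.1 names combined medication as something to analyse. No text says whether these patients count towards the 300, towards the 300 or more comparators, or separately, nor on which side of the capsule-versus-other contrast they fall.

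**5. The 24-hour rule.** The Note in Section 7 excludes movements within 24 hours of medication and does not say whether assigned medication counts. If it does, the loss depends on how many comparators use drugs, how often, and whether they already did at baseline, since response is a change from baseline. The documents give none of these, so I attach no figure.

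**The case against.** The strongest reply is that the only formal hypothesis is single-arm, that 8.2 does not forbid adjustment, and that baseline data and subgroup reporting (7.2, item 10) already provide for patient differences. The first part stands: nothing here touches the primary endpoint. The second is true, but silence is the gap: 8.2 neither prescribes nor excludes adjustment. On the third, item 10 concerns response to the capsule within subgroups and is not tied to a group comparison.

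Four stronger readings are tempting and are not supported.

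- A reader might infer that combination patients are placed nowhere. They are excluded from the primary endpoint and recognised as a category. Only the counts and the contrast are open.
- A reader might infer that CSBM response is not comparable between groups as defined, and that the comparison must favour the capsule. That requires the unstated reading that assigned medication counts. Section 4 also lists treatments that are not drugs, patients medicated at baseline could be under-counted at both times, and combination patients could lose counts too.
- A reader might bring in the conflict between 8.1 (primary endpoint imputed) and 8.3 (missing data not filled in). It is a separate issue. Section 8.1 does not impute secondary endpoints, so a contrast on a secondary endpoint is untouched by it.
- A reader might take the two paragraphs in 3.2 as rival designs. The second can be read as describing the capsule cohort only, and needs no more than editorial reconciliation.

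**Conclusion.** The omission is certain on the text: a comparative purpose, non-random treatment, no designated between-group endpoint, an incomplete place for combination patients, and no confounding control. It should be corrected before analysis, but it does not threaten the single-arm primary result.

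The size is illustrative. With the assumed severity shares and no true effect, an unadjusted test rejects 8% to 31% of the time at 300 per group with a 20-point response gap, and 6% to 11% with a 10-point gap, instead of 5%. With the imbalance reversed, a real 10-point benefit could be largely hidden. These figures rest on assumed severity shares, response rates and effect, and on exactly 300 per group, although the comparator cohort is a minimum and removing combination patients could shrink the capsule group. The CSBM measurement problem is a possibility that depends on an unstated rule.

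**What to change.** Add a short comparative analysis to 8.2.

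- **Groups:** by treatment prescribed at Visit 1 (capsule only, other only, combination), with capsule only v other only as the main contrast. State how combination patients count towards enrolment.
- **Endpoint:** name one from 7.2. If it is based on CSBM or SBM, state whether assigned medication counts under the Note in Section 7. Alternatively, use one measured alike in both groups, such as the PAC-QOL and PAC-SYM response in item 7, noting that it is self-reported by patients who know their treatment.
- **Estimate:** an adjusted risk difference with 95% confidence interval, by logistic regression with standardisation or by propensity-score weighting. Use baseline variables such as CSBM, scale scores, constipation type, baseline treatment, age, gender, BMI and site.
- **Reporting:** covariate balance and missing outcomes by group, with the unadjusted result as descriptive.

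If this is not wanted, one sentence is enough: the between-group comparison is descriptive and carries no p-values. Either way, tidy the duplicated text in 3.2.

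The cost is SAP wording and modest analysis work, because baseline status, treatment information and scales are already collected at Visit 1. The interval may widen somewhat. In the worst case illustrated (30% v 60% severe, 20-point gap), standardising for that one factor gives a half-width of 8.2 points against 8.0 at 300 per group, and 9.2 against 8.9 at 240. It would widen further with many covariates or once combination patients are removed. Subtyping tests are optional (7.1.1), so constipation type will be unevenly measured, and residual confounding will remain.

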7.2 Secondary Efficacy Endpoints

- 1) Proportion of constipated patients who use/do not use other constipation treatment methods during treatment and after the vibrating capsule treatment and at the end of follow-up;
- 2) Proportion of patients with an average increase of ≥ 1 CSBMs per week compared to the baseline period;
- 3) Proportion of respondents with an average of ≥ 3 SBMs per week during the treatment period;
- 4) Proportion of subjects with ≥ 3 SBMs per week and an increase of ≥ 1 CSBMs during at least 4 weeks of treatment compared to baseline;
- 5) Proportion of patients with an average increase of ≥ 1 CSBMs per week during the follow-up phase compared to the baseline period;
- 6) Proportion of patients with an average of ≥ 3 SBMs per week during the follow-up phase;
- 7) Proportion of patients with a reduction of ≥ 1 point in total PAC-QOL and PAC-SYM scores after treatment compared to the baseline period;
- 8) Proportion of patients with a reduction of ≥ 1 point in total PAC-QOL and PAC-SYM scores after follow-up compared to the baseline period;
- 9) Time of first use of laxative or enema after a course of vibrating capsule treatment (6 weeks);
- 10) Proportion of constipated patients (including different constipation types, occupations, age groups, BMI, gender, and baseline treatment status) responding to vibrating capsule treatment and at the end of follow-up.

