8.1 Statistical Analysis of the Population

Sample Size Calculation

H0: The effectiveness rate of vibrating capsule treatment for constipation $\leq 50\%$

H1: The effectiveness rate of vibrating capsule treatment for constipation $> 50\%$

In a single-group design, if the study goal is to evaluate the effectiveness of vibrating capsule

treatment for constipation and compare it with the expected 50% effectiveness rate, then a one-sample proportion test can be considered for sample size calculation.

Sample size calculation formula for single sample proportion test is:

$$n = \frac{\left[Z_{1-\alpha} \sqrt{P_0(1-P_0)} + Z_{\beta} \sqrt{P_T(1-P_T)} \right]^2}{(P_T - P_0)^2}$$

Where:

- (1) p is the overall expected success rate (here it is estimated that the effectiveness of treating constipation with vibrating capsules is 50%);
- (2) p_0 is the success rate under the null hypothesis (assuming a 40% success rate under the null hypothesis);
- (3) The probability of Type I error α is set to 0.05, and the probability of Type II error β is set to 0.2 (i.e., the statistical power is $1-\beta=0.8$);

At least 191 participants are needed for this study. Assuming a 20% loss to follow-up, the final sample size required is 239. Considering this is a real-world study and taking into account the outpatient volume of the participating center, it is planned to enroll 300 patients who will take vibrating capsules for 6 weeks, and at the same time, include ≥ 300 patients undergoing constipation treatment during the same period.

(1) Full Analysis Set (FAS) is the set of patients that is as close as possible to the ideal implied by the Intention-to-Treat principle. Specifically, in this trial, the FAS is the data set of all patients with baseline evaluation who take at least one capsule treatment/other treatment option. Missing data for primary efficacy endpoints in the FAS will be imputed according to certain rules while missing data for secondary efficacy endpoints will not be imputed.

(2) Per Protocol Set (PPS) is a subset of the FAS and refers to the set of subjects who meet the inclusion criteria, do not meet the exclusion criteria, complete the treatment, and have no protocol violations. Specifically, in this trial, the PPS includes the patients in the FAS who:

- a) complete the full treatment,
- b) meet the inclusion criteria and do not meet the exclusion criteria,
- c) have good compliance with capsule administration/other treatment, and

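### Section 8.2 calls any difference with p < 0.05 statistically significant, with no multiplicity control or exploratory label, although endpoint 10 opens at least 12 subgroup comparisons

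*Combined protocol and SAP*

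**What the plan says.** Section 8.2 (Statistical Analysis Principle) gives one general rule for difference tests: two-sided, alpha 0.05, and "if the p-value is <0.05, the difference is considered statistically significant".

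Item 10 of the secondary efficacy endpoints (section 7.2 and the Protocol Summary) is the proportion of patients "responding to vibrating capsule treatment and at the end of follow-up", broken down by "different constipation types, occupations, age groups, BMI, gender, and baseline treatment status". That is six factors at two times.

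Section 3.1 makes response by patient type part of the study's purpose: "to analyze the response of functional constipation patients with different severity, treatment status, capsule dosage, and combined medication to Vibrabot capsule". Severity, capsule dosage and combined medication are not among the six factors of item 10. The same section says that the study should "promote the establishment and application of consensus or guidelines for the use of Vibrabot capsule".

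The documents contain no multiplicity adjustment, testing hierarchy or interaction test, and nothing that marks subgroup or secondary results as exploratory. They also do not say how many subgroup tests will be run, or that each factor will be formally tested.

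**The concern.** A per-test threshold of 0.05 protects one test. Applied without adjustment to a family of comparisons, it lets the chance of at least one false finding grow with their number. Here the family includes a named secondary endpoint that looks across many patient characteristics, and the report may call every p-value below 0.05 significant.

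The stake is what the trial will be taken to have shown. Its results are meant to feed a consensus or guideline on using the capsule, and its purpose includes response by patient type. A chance difference between, say, occupational groups, reported as statistically significant under the plan's own rule, could enter that consensus as a finding.

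**Working it through.** **The plan's own figure.** The documents state no familywise error rate. Their alpha of 0.05 is sized for one test, as section 8.1 shows. With a null rate of 0.40, an expected rate of 0.50, 80% power and the two-sided quantile:

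n = [1.960 × √(0.40 × 0.60) + 0.842 × √(0.50 × 0.50)]² / 0.10² = 190.7, rounded up to the stated 191; and 191 / 0.80 = 238.75, rounded up to the stated 239.

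So the stated 191 corresponds to a two-sided 0.05 spent on a single primary test. (The 40% null differs from the 50% in the stated hypotheses; that is a separate matter.)

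**Inputs.**
- Threshold per test: 0.05, two-sided (8.2).
- Factors in item 10: constipation type, occupation, age group, BMI, gender, baseline treatment status = 6.
- Time points in item 10: after treatment and end of follow-up = 2.
- Extra factors in 3.1: severity, capsule dosage, combined medication = 3. Taking these at both time points is an assumption.
- Correlation between test statistics: not given. Assumed 0 to 1 between the two time points of one factor, and 0 to 0.5 between factors.
- Scenario: no factor affects response, and each factor is tested once per time point.

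**Independent tests.** The chance of at least one false positive in k tests is 1 − 0.95^k.
- Item 10, k = 6 × 2 = 12: 1 − 0.95¹² = 46.0%.
- With the three extra factors, k = 9 × 2 = 18: 1 − 0.95¹⁸ = 60.3%.
- The expected number of false positives is 12 × 0.05 = 0.6 and 18 × 0.05 = 0.9. These do not depend on correlation.

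**Allowing for the same patients at both times.** Pairs of correlated normal test statistics were simulated, with 1,000,000 replicates per scenario and factors independent of each other.

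| Correlation between time points | 12 tests | 18 tests |
|---|---|---|
| 0 | 46.0% | 60.3% |
| 0.5 | 43.6% | 57.6% |
| 0.7 | 40.7% | 54.4% |
| 0.8 | 38.6% | 51.9% |
| 0.9 | 35.4% | 48.1% |
| 1 (exact) | 1 − 0.95⁶ = 26.5% | 1 − 0.95⁹ = 37.0% |

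**Allowing also for correlation between factors.** With 12 tests, correlation of 0.2–0.5 between factors and 0.5–0.7 between time points, the result is 32–42% (400,000 replicates).

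**Direction of what is left out.** Pairwise contrasts between levels of a multi-level factor (constipation type, occupation, age group) would raise all these figures.

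**The case against.** The strongest reply is that item 10 is worded as a proportion, 8.2 presents count data as frequencies and percentages, and no subgroup test is listed. On that reading item 10 is descriptive and there is no family of tests. This stands in part: formal testing of each factor is an inference. But nothing in the plan says that the results are descriptive only, and any subgroup p-value that is produced falls under the unqualified rule in 8.2. If description is all that is intended, one sentence saying so settles the point.

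The second reply is that the size is easy to overstate. This stands too. There are several stronger readings that the documents do not support:
- *A false subgroup finding is about as likely as not, or probable.* For item 10 this would need about 13.5 independent tests (log 0.5 / log 0.95). There are 12, and each pair uses the same patients. Even odds are reached only by counting factors from the study purpose or contrasts between levels.
- *Adding cohort comparisons on items 2 to 8 gives 19 tests and 1 − 0.95¹⁹ = 62%.* These items overlap by construction: item 4 combines the criteria of items 2 and 3, and items 5, 6 and 8 repeat items 2, 3 and 7 at follow-up. No between-cohort test is stated for any of them, and they are not subgroup contrasts.
- *The factors are confounded in particular ways, or BMI will be cut into groups.* The documents state neither. They do leave the age groups undefined.

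**Conclusion.** The point holds. The rule in 8.2 is not merely silent on multiplicity: it states that any p below 0.05 is significant, so tests run under it carry an inflated chance of a false claim. For item 10 that chance is at most 46%, about 35–44% at assumed time-point correlations of 0.5–0.9, and about 26% at full correlation. With the factors in the study purpose it is about 37–60%. Across these scenarios it is roughly five to twelve times the nominal 5%, so the need for a change does not depend on which one applies.

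The figures rest on three assumptions: each factor is tested once per time point, no factor truly matters, and the correlations lie in the ranges shown. They support saying that a false subgroup claim is a substantial risk, not that one is likely.

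**What to change.** In section 8.2, reserve the term statistically significant for the single primary test. State that the secondary endpoints, the item 10 subgroups and the cohort comparisons will be reported as estimates with 95% confidence intervals, labelled exploratory, with no claim of significance.

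This costs a short wording change, with no extra patients, visits or data; section 8.4 already provides for explained and justified changes to the statistical plan. The real price is that the sponsor gives up significance claims for secondary findings. If it wants to keep such claims for item 10, it would need a rule set in advance. Bonferroni over 12 tests, for example, means 0.05 / 12 = 0.0042 per test and a familywise error of 4.9% if the tests are independent.

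A multivariable logistic model with age and BMI kept continuous may be added as an optional supportive analysis, reported as estimates with confidence intervals. It is not the multiplicity remedy: one joint test per factor per time point is still 6 × 2 = 12 tests. A complete-case model would also drop patients with any factor missing; the flow chart appears to make constipation subtyping optional, and 8.1 does not impute secondary endpoints.
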